## 9. Missing Data Handling

Primary analysis will be complete-case under ITT. If >5% of primary endpoint data are missing, multiple imputation by chained equations (MICE,  $m=20$ ) will be performed assuming missing at random (MAR), including baseline value, group, age, BMI, and other outcomes as predictors. Sensitivity analyses will compare complete-case and MI results. Last Observation Carried Forward (LOCF) will not be used.

## 10. Outliers, Data Cleaning, and Assumptions

Continuous outcomes will be screened for extreme values using studentized residuals ( $> |3|$ ), leverage, and Cook's distance. Suspected data-entry errors will be queried and corrected if verified. Valid outliers will be retained; robustness will be assessed using non-parametric methods and influence diagnostics.

## 11. Protocol Deviations

Major deviations include missing >2 consecutive training sessions (exercise arm), receiving non-study exercise training, or violating key eligibility criteria. A deviation log will be maintained. PP analyses will exclude major deviations; ITT remains primary.

## 12. Interim Analyses and Data Monitoring

No interim analyses or formal stopping rules were planned due to the short duration and minimal risk of the behavioral intervention.

## **13. Sample Size Considerations**

A total sample of 22 participants (11 per arm) was planned based on feasibility. No formal power calculation was performed; the study is powered for detecting moderate-to-large effects and intended as hypothesis-generating with controlled Type I error through multiplicity adjustment for co-primary endpoints.

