# 4. General Analysis Principles

All tests two-sided with  $\alpha = 0.05$ . Continuous variables summarized by mean $\pm$ SD (or median [IQR] if non-normal); categorical variables by counts and percentages. Assumptions checked by Shapiro-Wilk (normality) and Levene's test (homogeneity of variance). When assumptions are violated, appropriate transformations (e.g., log for hs-CRP) or non-parametric methods are used.

Effect sizes and precision will be reported: adjusted mean differences with 95% confidence intervals (CI) from ANCOVA; within-group standardized mean changes (Cohen's d); and partial  $\eta^2$  for ANCOVA.

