## 5. Primary Endpoint Analyses

**Endpoints:** Change in adiponectin; change in hs-CRP (baseline to 48 h post-intervention).

**Between-group comparison:** ANCOVA with post-intervention value as the dependent variable, treatment group as fixed effect, and baseline biomarker value as covariate. Secondary covariates (age, baseline BMI) may be included in sensitivity models.

**Within-group change:** Paired t-test (or Wilcoxon signed-rank if non-normal) for descriptive purposes.

**Assumption handling:** If normality is violated, log-transform hs-CRP; if variance heterogeneity persists, use robust standard errors or non-parametric Mann–Whitney U for change scores as sensitivity.

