## 6. Multiplicity Control

Two primary endpoints (adiponectin and hs-CRP) will control family-wise error at 0.05 using Holm–Bonferroni adjustment. Secondary outcomes are exploratory; nominal p-values will be reported with 95% CIs.

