## **15. Tables, Listings, and Figures (TLFs)**

Pre-specified TLFs include: CONSORT flow; baseline characteristics; primary and secondary endpoint summaries (means, SDs, mean change, 95% CIs); ANCOVA results (adjusted mean differences, SEs, 95% CIs, p-values, partial  $\eta^2$ ); correlation matrix; and adverse events (counts, percentages).

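### SAP section 13 calls the study powered for moderate-to-large effects although no power calculation was done; with 11 per arm, power for a 0.5 SD difference is about 13–34% unless the baseline–post correlation is very high

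*SAP*

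**What the plan says.** SAP section 13 sets the size on practical grounds: "A total sample of 22 participants (11 per arm) was planned based on feasibility". The next sentence reads "No formal power calculation was performed; the study is powered for detecting moderate-to-large effects and intended as hypothesis-generating", and goes on to mention Type I error control across the two primary endpoints.

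The design elements that determine power are elsewhere in the SAP:

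- Section 4 makes all tests two-sided at 0.05.
- Section 5 specifies the between-group comparison as "ANCOVA with post-intervention value as the dependent variable, treatment group as fixed effect, and baseline biomarker value as covariate".
- Section 6 says that the two primary endpoints, adiponectin and hs-CRP, "will control family-wise error at 0.05 using Holm–Bonferroni adjustment".
- Sections 4 and 15 plan estimates with intervals: "adjusted mean differences with 95% confidence intervals (CI) from ANCOVA" and "ANCOVA results (adjusted mean differences, SEs, 95% CIs, p-values".

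Neither the SAP nor the protocol overview gives a target difference, an SD for either biomarker, a baseline–post correlation or a power level.

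**The concern.** Two things are wrong with the sentence. It contradicts itself: having said "No formal power calculation was performed", it has no basis for "the study is powered for detecting moderate-to-large effects". This part needs no assumption. The property it claims also looks implausible at the moderate end for a trial of 22 people with two primary endpoints.

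What is at stake is interpretation. A reader who accepts that the trial was powered for moderate effects may take a non-significant adiponectin or hs-CRP result as evidence that no moderate effect exists. If power for such an effect is low, that inference fails.

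**Working it through.** There is no stated power figure to reproduce, so the check asks what power the SAP's own design gives.

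**Inputs from the SAP**
- n = 11 per arm (section 13). All 22 are taken as analysed, which favours the plan.
- Two-sided tests (section 4).
- ANCOVA with group and baseline (section 5): residual df = 22 − 3 = 19.
- Holm over two endpoints (section 6): first step at 0.05/2 = 0.025. The second step, at 0.05, is open only if the first succeeds.

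**Assumptions, because the documents are silent**
- Moderate = 0.5 SD and large = 0.8 SD, in units of the SD of the post-intervention value.
- Adequate power = 80%.
- Baseline–post correlation ρ unknown, shown from 0 to 0.9.

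**Formula.** Residual SD = √(1 − ρ²). Noncentrality = d/√(1 − ρ²) × √(11/2). Power comes from the noncentral t distribution with 19 df. The critical values are 2.433 at 0.025 and 2.093 at 0.05.

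Example: d = 0.5 and ρ = 0.8 give 0.5/0.6 × 2.345 = 1.954, hence power 33.9% at 0.025.

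| ρ | 0.5 SD, α 0.025 | 0.5 SD, α 0.05 | 0.8 SD, α 0.025 | 0.8 SD, α 0.05 |
|---|---|---|---|---|
| 0 | 12.7% | 20.0% | 31.3% | 42.9% |
| 0.5 | 16.5% | 25.1% | 41.4% | 53.8% |
| 0.7 | 24.0% | 34.5% | 58.4% | 70.3% |
| 0.8 | 33.9% | 45.8% | 75.0% | 84.3% |
| 0.85 | 43.6% | 56.1% | 86.0% | 92.2% |
| 0.9 | 60.6% | 72.3% | 96.2% | 98.3% |

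**Correlation needed for 80% power.** At ρ = 0 the design detects 1.41 SD with 80% power at 0.025, and 1.26 SD at 0.05. Call this value k. The detectable difference is then k√(1 − ρ²), so the correlation needed is ρ = √(1 − (d/k)²).
- d = 0.5: ρ = 0.935 at 0.025, or 0.918 at 0.05.
- d = 0.8: ρ = 0.823 at 0.025, or 0.772 at 0.05.

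**Difference detectable with 80% power**

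| ρ | 0 | 0.5 | 0.7 | 0.8 | 0.85 | 0.9 |
|---|---|---|---|---|---|---|
| α 0.025 | 1.41 SD | 1.22 | 1.01 | 0.85 | 0.74 | 0.61 |
| α 0.05 | 1.26 SD | 1.09 | 0.90 | 0.76 | 0.66 | 0.55 |

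**Full Holm procedure.** This was simulated with both effects at 0.5 SD and a between-endpoint correlation of 0 or 0.5 (assumed, with signs aligned). Power per endpoint is 13–37% for ρ from 0 to 0.8 and about 65% at 0.9. The chance that at least one endpoint is significant is about 20–54% for ρ from 0 to 0.8, and 75–83% at 0.9.

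**Robustness.** Simulating the ANCOVA with a random baseline gives slightly lower power for 0.5 SD at 0.025: 11.8%, 32.5% and 57.9% at ρ = 0, 0.8 and 0.9. The normal approximation gives slightly higher values: 14.3%, 38.7% and 67.3%. Neither reaches 80%.

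**Interval width.** Expected 95% CI half-width = 2.093 × √(2/11) × √(1 − ρ²). This is 0.89 SD at ρ = 0, 0.77 at 0.5, 0.64 at 0.7, 0.54 at 0.8 and 0.39 at 0.9. Up to ρ = 0.8 the half-width exceeds 0.5 SD, so an interval centred on zero would still include a moderate effect.

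**The case against.** The strongest reply is that the SAP contains no number to be wrong. It does not define moderate, name the effect metric or set a target power. The 0.5 SD and 80% benchmarks are brought in from outside, so the plan's statement is better called unsupported than miscalculated. This stands as a limit on wording, and the benchmarks are labelled as assumptions here. It does not rescue the claim. At a flat 0.05, which is more lenient than Holm, power for 0.5 SD is still only 72.3% at ρ = 0.9. A within-group standardised change of 0.5 with 11 participants has only about 32% power at 0.05.

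It can also be said that the phrase covers large effects, and that under Holm either endpoint may succeed alone. Both points have substance. Power for 0.8 SD is 75.0% at ρ = 0.8 and 96.2% at ρ = 0.9 for α = 0.025. The chance of at least one success at 0.5 SD can pass 80% at ρ = 0.9 if the endpoints are independent. But at ρ = 0.5 the power for 0.8 SD is only 41–54%, and at ρ = 0.8 or below the chance of at least one success at 0.5 SD is at most about 54%.

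Finally, the consequence is modest. The feasibility basis and exploratory purpose are disclosed, the clause drives no design choice, and the protocol overview describes the study as already conducted, so a correction affects reporting only. This is accepted. It limits the weight of the point but does not make the sentence correct.

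**Conclusion.** The concern holds. The self-contradiction in section 13 is a matter of the text alone. On the conventional reading of moderate as 0.5 SD, the trial has roughly one chance in eight to one in three of detecting such an effect on a given endpoint at the first Holm step, for ρ between 0 and 0.8. It does not reach 80% per endpoint unless ρ is about 0.93 or more. For ρ of 0.5 to 0.8, what it can detect with 80% power is about 0.85 to 1.2 SD. The large end of the claim is therefore attainable only with a high correlation.

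The exact figures depend on ρ, which the documents do not give; the conclusion for 0.5 SD holds across the whole range shown. The statements on feasibility, hypothesis generation and Type I error control are sound. This should be fixed, but it does not threaten the analysis.

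**What to change.** In SAP section 13, delete the clause "the study is powered for detecting moderate-to-large effects". Keep the statements that the size was set by feasibility, that no power calculation was done, and that the study is hypothesis-generating with multiplicity control. Deletion alone removes the error. It would help the reader to add, for example:

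> For illustration, assuming a baseline–post correlation of 0.5–0.8 (not known for this population), 11 per arm gives 80% power for differences of about 0.85–1.2 SD at the first Holm step of 0.025 (about 0.76–1.1 SD at 0.05), and about 17–34% power for 0.5 SD at 0.025. A non-significant result does not by itself exclude moderate effects; the 95% confidence intervals show which effects remain compatible with the data.

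The added text should be marked as illustrative and as written after the design was set, so that it is not mistaken for a prospective calculation.

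The cost is one clause of wording. Sample size, model, alpha and analysis sets stay as they are, and no further enrolment is proposed. The only drawback is that the stated sensitivity becomes less favourable.

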## **14. Statistical Software**

Analyses will be performed using SPSS version 17.0. Where applicable, confirmatory and sensitivity analyses may be replicated in R (version  $\geq 4.0$ ).

## **15. Tables, Listings, and Figures (TLFs)**

Pre-specified TLFs include: CONSORT flow; baseline characteristics; primary and secondary endpoint summaries (means, SDs, mean change, 95% CIs); ANCOVA results (adjusted mean differences, SEs, 95% CIs, p-values, partial  $\eta^2$ ); correlation matrix; and adverse events (counts, percentages).

## **16. Data Presentation Standards**

Report means with one decimal where appropriate; hs-CRP to two decimals; exact p-values to three decimals (e.g., p=0.047). Confidence intervals at 95% two-sided. Units consistent with laboratory reports (adiponectin  $\mu\text{g/mL}$ ; hs-CRP  $\text{mg/dL}$ ).

